Pittsburgh Sleep Quality Index (PSQI)		X				X	X	
Associated Symptom PROMs: BFI, CFS, BDI		X				X	X	
QOL PROMs: FACT-Br		X				X	X	
Neuro-cognitive Battery		X					X	
Standard of Care MR Brain ^a	X						X ^j	

¹ Patient's undergoing telehealth assessment at the pre-screening timepoint require virtual examination by observation only. Blood draw and laboratory testing can be performed locally and reviewed remotely.

^a Pre-study requirements listed in table must be completed **within** 21 days prior to registration.

^b Blood pressure (mmHg), heart rate (BPM)

^c Height, Weight, M² Patients undergoing telehealth assessment can provide this information verbally using home device (e.g. scale).

^d Albumin, alkaline phosphatase, total bilirubin, bicarbonate, BUN, calcium, chloride, creatinine, glucose, potassium, total protein, SGOT[AST], SGPT[ALT], sodium.

^e Serum pregnancy test (women of childbearing potential).

^f May be performed by telephone.

^g Epworth Sleepiness Scale (ESS) will be completed either in the clinic (D1, D29, D70) at each of the study visits (V1, V2, V3) or by telephone (D8, D15, D22) during the flexible dose escalation portion of the study.

^h 7-day sleep diary is to be completed at baseline (D1-7), continuously during dose escalation (D8-14, D15-21, D22-28), and during the first and last week of fixed dose drug continuation (~D29-35 and ~D63-70). Actigraphy will be collected continuously.

ⁱ Patients may complete the baseline sleep diary and actigraphy prior to the Baseline Visit (V1) or after the Baseline Visit (V1).

^j Post-treatment MR Brain is to be performed D85 \pm 42 days.

^k Study visits may be conducted via telehealth visit. Blood draw and EKG (when appropriate) can be performed locally and reviewed remotely.

3. Screening

Glioma patients seen at the Wake Forest Baptist Medical Center will be considered for eligibility at or before their scheduled visits. In general, patients may be approached at the time of routine outpatient visit for follow up with neuro-oncology, medical oncology, radiation oncology, and neurosurgery.

Patients who are identified as potential study candidates will have an opportunity to hear about the study and complete written informed consent. Patients who sign informed consent and do not meet eligibility criteria will be considered screen failures, will not be evaluable for the primary endpoint, will not count toward the total sample size, and this enrollment will be replaced.

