Adverse events will be assessed by telephone call completed on D8+1 day, D15+1 day, and D22+1 day. Patients will be assessed in clinic at D29+7 days. Patients who report a symptomatic dose-limiting toxicity will de-escalate treatment back to the highest previously tolerated dose and will be seen for V2.

6. Fixed Dose Drug Continuation

At the completion of the flexible dose titration, patients will be seen for a routine study visit (V2) or via telehealth visit to document adverse events at the completion of flexible dosing, review sleep diary and actigraphy, and complete V2 assessments. Data from this interim time point may be used to clarify the trajectory of improvement, decline, and no change in study assessments. Patients will then proceed with fixed dose treatment at 300 mg p.o. once daily or the maximum tolerated dose for that patient.

Fixed dose drug continuation will be continued for 6 weeks. Patients will complete a sleep diary for the first 7 and last 7 days of fixed dose treatment; actigraphy will be collected continuously. At the completion of fixed dose treatment, patients will be seen for V3 study assessments (Section 6.7).

7. 30 Day Follow Up

All patients will be followed for 30 days following the completion of treatment to assess for delayed toxicity. Adverse events will be recorded at this 30 day follow up visit. If the patient is unable to return for this visit, adverse events will be recorded by telephone or telehealth visit.

8. Study Assessments

Assessment of sleep, neuro-cognitive function, fatigue, mood and quality of life will be assessed at baseline (V1) and at the end of the fixed-dose drug continuation phase of the study (V3). Given that patient drop out could occur during the course of the study treatment, study assessments that are not subject to significant practice and/or repeated measure effects will also be assessed after the flexible dose titration period (V2).

The following assessments will be performed:

1. Patient-reported outcome measures (PROMs) for sleep:

Changes in patient-reported outcomes measures (PROMs) are pivotal to cancer control drug approval.

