In the absence of treatment delays due to adverse events, treatment may continue for the duration of the study treatment (D70 +7 days) or until one of the following criteria applies:

- Disease progression requiring surgery or radiation therapy,
- Intercurrent illness that prevents further administration of treatment,
- Unacceptable adverse event(s),
- Patient decides to withdraw from the study, or
- General or specific changes in the patient's condition render the patient unacceptable for further treatment in the judgment of the investigator.

12. Duration of Follow Up

Patients will be followed for a minimum of 30 days after the last study drug is administered for adverse events monitoring.

13. Determination of Evaluable Patients

Patients who enroll in the study but do not take a dose of the study medication will not be considered evaluable and will be replaced. In other words, patients who begin the pre-treatment baseline assessment and do not take the study medication will not be evaluable and will be replaced.

14. Criteria for Removal from Study

Patients will be removed from study when any of the criteria listed in section 5.4 applies.

8 Dosing Delays/Dose Modifications

During the flexible dose titration period of this study, dose modifications will be performed according to the Dose-Limiting Toxicity scheme outlined in Section 6.9.1.

During the fixed dose drug continuation period of this study, for patients who experience a new dose-limiting toxicity (see Section 6.9.1) treatment dose will be modified according to the following scheme:

Dose Level	Insert Agent Name Dose
+1	75 mg, p.o. once daily
+2	150 mg, p.o. once daily
+3	300 mg, p.o. once daily

All dose modifications will be recorded, tracked and monitored via a drug diary (Appendices F and G) throughout the duration of study treatment.

9 Measurement of Effect

Tumor response and survival outcomes will NOT be included as an endpoint in this study. MRI Brain is included to track evidence of clinically documented progressive disease which could contribute to changes in patient-reported and clinician assessed outcome measures (see Section 7.8).

10 Adverse Events List and Reporting Requirements

1. Adverse Event List for solriamfetol

In the 12-week placebo-controlled studies in patients with narcolepsy and OSA, in the overall population the most frequent ($\geq 5\%$) adverse events that also had a higher incidence with solriamfetol than with placebo were:

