Storage Requirements: solriamfetol tablets are to be stored at room-temperature conditions, 15°C to 30°C (59°F to 86°F).

Stability: Studies are ongoing to monitor the stability of solriamfetol tablets.

12 Data Management

Informed consent document	EPIC
Protocol registration form	OnCore
Adverse Events Log (Appendix E)	OnCore
Patient Drug Diary (Appendix F)	
Fixed Dose Patient Drug Diary (Appendix G)	
Epworth Sleepiness Scale (Appendix H)	
Pittsburgh Sleep Quality Index (Appendix I)	
Brief Fatigue Inventory (Appendix J)	
Cancer Fatigue Scale (Appendix K)	
Beck's Depression Inventory (Appendix L)	
Neurocognitive Battery Form (Appendix M)	
FACT-Br (Appendix N)	
Concurrent Medication (Appendix O)	OnCore
Off-Study Form (Appendix P)	OnCore
MR Imaging Record (Appendix Q)	
Sleep Diary and Actigraphy Record (Appendix R)	
Glioma History (Appendix S)	

13 Statistical Considerations

This is a single-arm, open label, non-randomized safety study in patients with stable glioma disease. The primary outcome is safety of oral solriamfetol as doses of 75 mg daily, 150 mg daily and 300 mg daily. Secondary outcomes include ESS score, PSQI score, a composite neurocognitive battery score, FSS score, BDI score, and FACT-Br score.

1. Analysis of Primary Objective

For the primary outcome, NCI Common Terminology Criteria for Adverse Events (CTCAE) version 5.0 will be used for scoring toxicity and adverse events.

The severity and frequency of toxicity and adverse events for each dose of solriamfetol will be tabulated using descriptive statistics. The proportions of subjects who experienced grade 3 or above toxicities will be estimated, along with 95% confidence intervals by each type of toxicity.

To compare the safety of solriamfetol at 75 mg daily, 150 mg daily, 300 mg daily, chi-squared statistics will be used. If there are some cells with expected value <5 , Fisher's exact test will be used for the comparison.

2. Analysis of Secondary Objective

For the secondary outcomes, descriptive statistics will be performed for each of the outcome measures. Changes in pre- and post-treatment scores will be assessed and compared using the pair-t tests if the changes follow a normal distribution and using the Wilcoxon signed rank tests if the changes do not follow a normal distribution. For the comparison between the change in ESS score in the study patients and the published change score in patients with obstructive sleep apnea, we will use the one sample t-test for this comparison.

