3. Analysis of Exploratory Objective

13.3.1 To explore the dose response effect of solriamfetol on actigraphy, linear regression models will be used where the dosage will be treated as an ordinal variable.

Transformation of actigraphy will be performed to satisfy the normality assumption if needed.

13.3.2 The analysis will be the same as that specified in 13.1.

4. Power and Sample Size

We plan to recruit around 36 participants.

In the prior phase 2a and phase 2b studies in patients with narcolepsy which had similar sample sizes, no patients in the phase 2a and three patients in the phase 2b study required discontinuation of study medication, though two of these discontinuations were not attributed to the study drug.^{46,47} In the prior phase 3 study, 9 patients (9%) including one in the 75 mg arm, 3 in the 150 mg arm, and 5 in the 300 mg arm required discontinuation due to treatment related AEs.⁴⁵ In the current study, 36 patients will receive 75 mg daily dosing. We conservatively estimate that at least 33 patients will escalate to 150 mg daily, and at least 30 patients will escalate to receive 300 mg daily. These estimates are felt to be overly conservative based on data from these prior studies in patients narcolepsy.

From prior studies, the most common adverse event proportions range from 10% to 20%. Assuming 10% and 20% of adverse event proportion, the detectable proportions for the combined dosage are 24% and 36%, respectively, in order to reach 80% power at a significance level of 0.1 (given the pilot nature of this study) and a two-sided test. These detectable proportions are reasonable. If we observe an adverse event proportion in the patients with primary gliomas that is higher than 36%, then the adverse event proportion is significantly higher than the other study populations. In practice, if an adverse event proportion is higher than 50%, then the safety/tolerability of solriamfetol needs to be questioned. We should have enough power for this primary analysis. Note that this study allows us to determine safety profiles for the 3 doses of solriamfetol. It is primarily for descriptive purpose and to generate data on safety and estimation of effect size for the design of a subsequent randomized study powered to determine drug activity. The results generated from this study will be beneficial for the future research study.

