ESS score is the most important secondary outcome in this study. We also calculate the power to test whether the pre-post change is different from 0 and test whether the change is different from the pre-post change in the prior studies which recorded the pre-post changes for patients at 75 mg, 150 mg, and 300 mg. At an alpha of 0.10, a two-sided test, and cohort sample size of 36 patients, the study will have 80% power to detect the mean difference of 1.01 point ($=0.42$ standard deviation (SD)) in ESS score from the study sample. The mean differences are reasonable. We should have enough power for our analysis.

Prior studies of solriamfetol in patients with narcolepsy have demonstrated improvement in ESS scores at Week 8 of -3.4 (75 mg daily), -5.2 (150 mg daily), -6.4 (300 mg daily), and -2.1 (placebo) with baseline ESS ranging from 16.9-17.3. In patients with OSA, Week 8 improvements were -6.3 (75 mg daily), -6.9 (150 mg daily), -7.7 (300 mg daily), and -3.8 (placebo) in patients with baseline ESS ranging from 14.8 to 15.6. In our prior study mean ESS score for patients with primary brain tumors who would be eligible for the proposed study (i.e. ESS \geq 10) was 14.8 (SD: 2.4). For the current study, we will use the data from the prior OSA study as a comparator given that baseline ESS scores were similar to what we anticipate in the to-be-enrolled cohort. Based on this, the study hypothesizes that treatment with solriamfetol at 75 mg, 150 mg, or 300 mg will achieve at least a 6.3 point difference (75 mg daily) and up to 7.7 point difference (300 mg daily) in ESS scores at Week 10 (baseline vs V3). This will be compared to a null difference of 3.8 (placebo arm in OSA study). This mean change in ESS scores is clinically meaningful as has been reported.⁵³ In order to detect the differences between the mean change ESS score from the proposed study to the mean change of 3.8 in the placebo arm in OSA study, the detectable mean change needs to be greater than 5.4 in the study sample in order to reach 80% power. We hypothesize that the mean change in this study sample ranges from 6.3 to 7.7, which is higher than 5.4. We should have sufficient power to detect the difference between the mean change ESS score in our study sample and that in the placebo arm in the OSA study.

5. Estimated Accrual Rate

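### By implication, the change tests in 13.2 leave out treated patients without a V3 score, and Section 13 does not use V2; a three-visit model on scheduled data is a cheap improvement (minor)

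*Combined protocol and SAP*

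**What the plan says.** **Tests.** Section 13.2 reads "Changes in pre- and post-treatment scores will be assessed and compared using the pair-t tests if the changes follow a normal distribution", with the Wilcoxon signed rank test otherwise. For ESS change against the published OSA change, "we will use the one sample t-test for this comparison". It also plans descriptive statistics for each measure, without naming visits.

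**Contrast and purpose.** Section 13.4 hypothesises at least 6.3 and "up to 7.7 point difference (300 mg daily) in ESS scores at Week 10 (baseline vs V3", and compares this with 3.8, the OSA placebo change. It ranks ESS first among the secondary outcomes. It says the study should also give "estimation of effect size for the design of a subsequent randomized study powered to determine drug activity".

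**V2 and telephone scores.** Section 7.8 explains why some measures are repeated at V2: "Given that patient drop out could occur during the course of the study treatment, study assessments that are not subject to significant practice" effects are also taken after titration. Section 7.6 gives the only stated use: "Data from this interim time point may be used to clarify the trajectory of improvement, decline, and no change in study assessments". ESS is also taken "by telephone (D8, D15, D22) during the flexible dose escalation portion of the study" (Section 7.2, footnote g).

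**Replacement.** Under Section 7.13, patients who enrol but "do not take a dose of the study medication will not be considered evaluable and will be replaced". Nothing provides for replacing a patient who was dosed and lost later.

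Section 13 gives no rule for a missing V3, no analysis set for the secondary outcomes, no sensitivity analysis and no role for V2 or the telephone scores.

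**The concern.** A paired or one-sample change test needs both scores. With no rule for a missing V3, a treated patient without one drops out of the analysis, even if a V2 score exists. The protocol foresaw drop-out and scheduled V2 with that in mind, but this purpose never reaches the analysis section.

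If patients who improve less are more likely to be missing at V3, those who remain look better than the treated group as a whole. There is no control arm in which similar loss could offset this. At stake is the size of the ESS change, which 13.4 wants for planning a later trial.

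**Working it through.** **1. The plan's own figure.** For a one-sample t-test with n = 36, two-sided alpha 0.10, 80% power and SD 2.4, the noncentral t gives 0.423 SD, and 0.423 × 2.4 = 1.01 points. This matches the 1.01 points (0.42 SD) in 13.4. It needs all 36 patients to have V3. With 30 it becomes 0.465 × 2.4 = 1.12 points, so the loss of precision is modest.

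**2. Bias identity.** Completer mean − mean of all treated = loss fraction × (completer mean − mean of those lost). If those lost improve as much as the others, this is zero at any loss rate.

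**3. Inputs.**
- Change SD: not in the documents. The 2.4 in 13.4 is the SD of ESS scores, not of change. Assumed range: 2.4 × √2 = 3.4, up to 5.
- Correlation between V2 and V3 change: assumed 0.6.
- Loss before V3: not in the documents. Illustrated at 6%, 17% and 32%. At 17%, about 30 of 36 remain.
- Response-driven share: assumed 40%, the rest random. The nearest figure in the documents is lack of efficacy in 6 of about 16 discontinuations at 300 mg in the narcolepsy phase 3 study (10.2/27.1 = 38%, Section 1.5.1).
- Response-driven loss follows a logistic curve in the V2 change, slope 1 or 2 per SD; all loss is placed after V2.

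**4. Completer overstatement of the mean change, in points (simulation, 2,000,000 patients).**

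| Loss | SD 3.4, slope 1 / 2 | SD 5, slope 1 / 2 |
|---|---|---|
| 6% | 0.044 / 0.079 | 0.065 / 0.116 |
| 17% | 0.125 / 0.205 | 0.185 / 0.302 |
| 32% | 0.231 / 0.361 | 0.339 / 0.530 |

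By the identity, the 17% row implies that those lost improve less than completers by 0.125/0.17 = 0.7 to 0.302/0.17 = 1.8 points. If all loss were response-driven, the overstatement at 17% would be 0.30 to 0.68 points.

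**5. Against sampling error.** With 30 completers the standard error is 3.4/√30 = 0.62 or 5/√30 = 0.91. The 17% overstatement is a fifth to a third of this (0.125/0.62 = 0.20; 0.302/0.91 = 0.33).

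**6. Against the test.** At a change of 6.3, t = (6.3 − 3.8)/0.62 = 4.0 or 2.5/0.91 = 2.7, against a critical value of about 1.70 on 29 degrees of freedom. If 0.30 of an observed 6.3 were bias, (6.0 − 3.8)/0.91 = 2.4 would still exceed it. Only if the true change were 3.8 would the test suffer: at 17% loss, the upper-tail error rises from 5% to about 8-9%.

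**7. What V2 recovers.** When loss depends only on the V2 score, a likelihood model on V2 and V3 leaves a bias of 0.01 or less. When it depends on the unseen V3 score (17% loss, 40% share), the overstatement falls only from 0.22-0.52 to 0.14-0.35. Precision is almost unchanged: standard error 0.61 for the model and 0.61-0.62 for completers at SD 3.4.

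**The case against.** **The effect is small and conditional.** This stands. At 17% loss it is about 2-5% of a 6.3-point change (0.125/6.3 to 0.302/6.3) and well under half a standard error. Section 13.4 calls the study mainly descriptive. Suppose the later trial took its effect as this change minus 3.8, which the documents do not say. An overstatement of 0.30 would then make that trial 1 − (2.5/2.80)² = 20% too small, but an estimate high by one standard error through chance would make it 1 − (2.5/3.11)² = 35% too small.

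**The response-driven share is borrowed.** This also stands. The 6 of 16 comes from one fixed-dose 300 mg narcolepsy arm over 12 weeks, whereas this trial continues at a patient-specific tolerated dose. The 32% drop-out in the modafinil study (Section 1.3) was mostly for side effects, which could bias the estimate either way. No document shows poorer responders being lost more often in glioma.

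**Stronger readings that the documents do not support:**
- That the plan declares a completers-only analysis. It does not; that is inferred from the choice of tests and the missing rule.
- That V2 has no role at all. This is true only of Section 13; 7.8 and 7.6 give it a purpose and an optional use.
- That earlier discontinuation rates forecast missing V3 scores. Appendix P allows withdrawal from drug only, so a patient who stops drug may still give V3.
- That most loss would come before V2, where V2 cannot help. The OSA withdrawal study lost 17 patients in titration and 9 in the stable-dose phase, but each phase lasted 2 weeks. Here titration lasts about 3 weeks and fixed dosing 6. Section 7.5 also sends patients with a dose-limiting toxicity in titration to V2; only one at 75 mg ends treatment (7.9.1).

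**Conclusion.** The point holds as a minor one. The planned tests leave out treated patients without V3, nothing replaces those patients, and Section 13 does not use the V2 scores that were scheduled with drop-out in mind. The ESS change is overstated only if poorer responders are lost more often. Under the assumptions above (17% loss, 40% response-driven, correlation 0.6, change SD 3.4 to 5, loss after V2) the overstatement is about 0.1 to 0.3 points; with loss unrelated to response it is zero. A reader might infer that the ESS comparison is unsound. It is not: at the hypothesised 6.3 to 7.7 the result against 3.8 stays the same. The reason to act is that a better estimate for the later trial can be had from data already scheduled.

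**What to change.** In 13.2:

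1. For ESS, BFI, CFS, BDI and FACT-Br, estimate the V3-minus-baseline change and its confidence interval from a repeated-measures model on baseline, V2 and V3, in all patients who took at least one dose. Use visit as a factor and an unstructured 3 × 3 covariance.
2. Use the ESS estimate and standard error from this model for the OSA comparison.
3. Name a fallback in advance that lets variances differ by visit, such as heterogeneous compound symmetry. Equal variances would fit poorly, because entry restricts baseline ESS to 10 or more.
4. Keep the paired t, Wilcoxon and one-sample tests as completer sensitivity analyses.
5. Add one ESS sensitivity analysis that also uses the D15 and D22 telephone scores. They belong to the lower titration doses, and a five-visit unstructured model (15 covariance parameters) is too heavy as the main analysis for 36 patients.
6. State one target for patients who stop drug, including whether V3 scores taken off drug count.
7. Report missing V2 and V3 by reason.

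The neurocognitive battery, taken at V1 and V3 only, stays paired. PSQI is not in the list, since its one-month recall at V2 reaches back before the first dose.

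The cost is analysis wording and a standard model, with no new visits. The downsides are slightly more modelling and reliance on missing at random, which only partly corrects loss that depends on the unseen V3 score.

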Secondary hypotheses include that solriamfetol treatment at maximal patient specific dosing will result in improvements in patient-reported excessive daytime sleepiness and sleep quality (e.g. ESS and PSQI), neurocognitive function (see below for neurocognitive battery), fatigue and mood (e.g. Brief Fatigue Inventory, Cancer Fatigue Scale, Beck Depression Inventory), and quality of life (FACT-Brain).

3. Exploratory Hypotheses

Improvements in objective measures of sleep (e.g. actigraphy, sleep diary) will be similar to those reported in prior studies (e.g. obstructive sleep apnea, narcolepsy). We hypothesize that improvements in sleep, neurocognition, fatigue, mood, and quality of life may vary by clinical factors such as corticosteroid use, antiepileptic use, and tumor grade by World Health Organization (WHO) classification.

3 Objectives

1. Primary Objective(s)

1. To estimate the safety of solriamfetol at 75 mg daily, 150 mg daily, 300 mg daily as assessed by NCI CTC Adverse Events (v5.0) in patients with primary gliomas compared to prior studies⁴⁵⁻⁴⁷

2. Secondary Objective(s)

1. To estimate the effect of solriamfetol on sleep by Epworth Sleepiness Scores (ESS) scores in patients with primary gliomas and compare the effect to previously published scores in patients with OSA
2. To estimate the effect of solriamfetol on sleep quality by Pittsburgh Sleep Quality Index scores
3. To estimate the effect of solriamfetol on neurocognitive function based on a disease-specific neurocognitive battery (see neurocognitive battery below)
4. To estimate the effect of solriamfetol on patient-reported fatigue (Brief Fatigue Inventory, Cancer Fatigue Scale) & mood (Beck's Depression Inventory)
5. To estimate the effect of solriamfetol on patient-reported QOL (FACT-Br)
6. To estimate the effect of solriamfetol on objective sleep-wake times by actigraphy and sleep diary (pre- vs post-treatment)

3. Exploratory Objective(s)

1. To explore a biologic gradient effect of increasing doses of solriamfetol on actigraphy
2. To explore differences in clinical activity of solriamfetol by corticosteroid use, antiepileptic use, and tumor grade

4 Patient Selection

Inclusion and exclusion criteria represent standard criteria for other sleep studies in this population (e.g. inclusion criteria) and standard exclusions for prior studies of this agent (e.g. exclusion criteria).^{8,39,40}

1. Inclusion Criteria

1. WHO Grade 2-4 infiltrating glioma by histologic confirmation

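### The one-sample t-test of ESS change against a published OSA mean leaves out that mean's sampling error if the result is claimed as a difference from an OSA arm, and the detectable change of 5.4 does not follow from the stated inputs

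*Combined protocol and SAP*

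**What the plan says.** Objective 1 in section 3.2 is to estimate the effect on ESS and "compare the effect to previously published scores in patients with OSA". Section 13.2 gives the method: "we will use the one sample t-test for this comparison". It does not state the arm, week or value.

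Section 13.4 adds three statements:

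- Power is considered for a test against zero and for a second test, to "test whether the change is different from the pre-post change in the prior studies which recorded the pre-post changes" at 75, 150 and 300 mg.
- The hypothesised change is 6.3 to 7.7 points, and "This will be compared to a null difference of 3.8 (placebo arm in OSA study").
- The paragraph ends by claiming sufficient power for the "difference between the mean change ESS score in our study sample and that in the placebo arm in the OSA study".

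Two detectable values are given. With alpha 0.10 two-sided and 36 patients, "the study will have 80% power to detect the mean difference of 1.01 point" (0.42 SD). Against 3.8, "the detectable mean change needs to be greater than 5.4 in the study sample in order to reach 80% power".

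Table 4 in section 1.5.2 shows that 3.8 is the Week 8 least-squares mean change on placebo. It gives arm sizes but no SD or standard error.

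**The concern.** A one-sample t-test treats the reference value as known without error. The OSA values are themselves estimates, from 58 to 116 patients per arm. If the report says that glioma patients changed more than the OSA placebo arm, or differently from an active arm, the standard error should include both sources of error. Otherwise the p-value is too small for the claim.

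The direction depends on the arm. Against placebo, the overstatement favours the drug. Against the active arms, it makes a difference from OSA easier to declare, which works against the plan's own expectation of 6.3 to 7.7, since those are the OSA active-arm changes at 75 mg and 300 mg.

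Section 13.4 calls ESS the most important secondary outcome and says that the study should support "estimation of effect size for the design of a subsequent randomized study". An estimated difference carried into that design should show its full uncertainty.

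**Working it through.** **Inputs.** From 13.4: N=36, two-sided alpha 0.10, power 80%, null 3.8, hypothesised change 6.3 to 7.7, SD 2.4. That SD describes ESS scores in an earlier cross-sectional sample, not change. From Table 4: placebo n=114, 75 mg n=58, 150 mg n=116, 300 mg n=115. Assumed: all 36 patients analysed, and a ratio r of OSA SD to trial SD of 1, varied from 0.5 to 2.

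**1. The plan's 1.01.** A one-sample noncentral t calculation with N=36, alpha 0.10 and 80% power gives 0.423 SD. With SD 2.4 this is 0.423 × 2.4 = 1.01 points, so the figure reproduces.

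**2. The plan's 5.4.** With the same inputs the threshold against 3.8 is 3.8 + 1.01 = 4.81, not 5.4. Power at 5.4 would be 98.9%. Counting the placebo arm's error (36 v 114, equal SD 2.4) gives 3.8 + 1.15 = 4.95. Several unstated bases come close to 5.4:

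| Test | SD of change | Alpha | Detectable mean |
|---|---|---|---|
| One-sample | 3.79 | 0.10 | 5.40 |
| One-sample | 3.39 (2.4 × √2) | 0.05 | 5.43 |
| Two-sample, 36 v 114 | 3.39 | 0.10 | 5.42 |

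The text does not show which, if any, was used. The SD of 3.79 is obtained by solving back from 5.4.

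**3. Error of the one-sample test for a difference from an arm.** Let the OSA arm have m patients. When the true means are equal, the one-sample statistic is distributed as k × t(35), with k = √(1 + r² × 36/m). The real two-sided error is 2 × P(t(35) > 1.690/k).

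| OSA arm | m | k at r=1 | Error at r=1 | Error at r=0.5 | Error at r=2 |
|---|---|---|---|---|---|
| Placebo | 114 | 1.147 | 15.0% | 11.3% | 26.9% |
| 150 mg | 116 | 1.145 | 14.9% | 11.3% | 26.7% |
| 300 mg | 115 | 1.146 | 14.9% | 11.3% | 26.8% |
| 75 mg | 58 | 1.273 | 19.3% | 12.5% | 37.2% |

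Simulation agrees: 14.9% (placebo) and 19.3% (75 mg) at r=1. A Welch test holds 9.8% to 10.0% for m=114 and m=58 at r = 0.5, 1 and 2. If 3.8 is a fixed number, k = 1 and the error is 10%.

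**4. Practical size against placebo (r=1).** The one-sample cut-off is 3.8 + 1.690 × SD/6. The Welch cut-off is 3.8 + 1.671 × SD × √(1/36 + 1/114).

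| SD of change | One-sample cut-off | Welch cut-off | Power at 6.3, one-sample | Power at 6.3, two-sample |
|---|---|---|---|---|
| 2.4 | 4.48 | 4.57 | >99.9% | >99.9% |
| 3.79 | 4.87 | 5.01 | 98.7% | about 96% |
| 5 (assumed) | 5.21 | 5.40 | 90% | 83% |

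**5. Interval width (r=1).** The ratio of 90% half-widths, Welch to one-sample, is 1.135 for placebo, about 1.13 for 150 and 300 mg, and 1.255 for 75 mg.

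**The case against.** The best defence is that 13.4 already settles the matter: it names the placebo arm, gives 3.8 and uses it as the null value. A one-sample test fits that and keeps its 10% level. The closing phrase about a difference from the placebo arm may be loose wording for the same test. Section 13.2 plans no interval for this comparison, no decision depends on it, and the study is described as mainly descriptive.

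Much of this stands. A reader of 13.2 alone might infer that the plan never identifies its comparator, or that the one-sample test is invalid. The documents support neither: 13.4 identifies the comparator, and the test is sound for a fixed benchmark. A reader might also infer that the error always favours the drug. It does so only for placebo, so the 19% for 75 mg is not evidence of bias towards benefit.

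What remains is that objective 1 in 3.2 and the end of 13.4 describe comparisons with OSA patients' results rather than with a constant, and 13.4 keeps the active doses open as comparators. For those claims the omitted error is real. The defence also leaves the 5.4 unexplained.

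**Conclusion.** The point holds in a limited form. If the result is presented as a difference from an OSA arm, the planned test overstates significance: about 15% error against a nominal 10% for placebo, 150 mg and 300 mg, and about 19% for 75 mg. These figures assume equal SDs and all 36 patients analysed. They would be lower or higher for other SD ratios, and the documents give none.

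The consequence for the placebo comparison is small. The cut-off moves by 0.09 to 0.14 point for SDs of 2.4 to 3.79, and power at 6.3 stays at about 96% or more. Only a larger assumed SD, such as 5, gives a noticeable loss (90% to 83%).

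A reader might take the 5.4 as a sign that the study is underpowered or that a two-sample calculation was done. Neither can be concluded: 5.4 is more cautious than the stated inputs require, and several bases fit it. It does need an explanation.

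**What to change.** 1. In 13.2, carry over the OSA placebo arm as comparator with its value and week, and say whether the active arms are also compared.
2. For any claim of a difference from an OSA arm, use a Welch-type comparison from summary statistics, SE = √(s²/n + published SE²), with a 90% confidence interval.
3. Otherwise keep the one-sample test, call 3.8 a fixed benchmark, and remove the claim of a difference from the placebo arm.
4. Restate 5.4 with its SD, alpha and test. With SD 2.4, alpha 0.10 and N=36 it is 4.81 one-sample, or about 4.95 two-sample at equal SDs. If a larger SD of change was used, give it.
5. State in the report what the change does not cure: known OSA is an exclusion criterion, so the populations differ; the OSA value is from Week 8 and the trial's from Week 10; the OSA value is a least-squares mean; and drug effect is not separated from placebo response.

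The cost is wording and, for option 2, looking up the published standard error for each arm compared. At equal SDs the 90% interval becomes about 13% wider against placebo, 150 mg or 300 mg and about 25% wider against 75 mg. No change in patients, visits or sample size is needed. The fixed-benchmark option costs wording only.
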